### 10.2 General Statistical Considerations

The following standards will be applied for the analyses unless otherwise specified.

Simple summary statistics (descriptive statistics) for continuous data will be n (number of non-missing observations), mean, median, standard deviation, minimum, and maximum.

The frequency count and percentage will be used to summarize categorical data. Summary statistics will be presented by treatment by period and overall.

Summary statistics for all safety and efficacy variables will be presented by sequence, except for tables related to incidence of AEs which will be presented by treatment group.

All tables of baseline and demographic data will be presented by sequence.

All data collected will be presented in the by-patient data listings, sorted by patient and by period and day, where appropriate.

P-values < 0.05 will be considered as statistically significant.

95% confidence interval will be calculated as appropriate.

Change From Baseline (CFB) will be summarized for efficacy and safety assessments, where Baseline is defined as Day 0.

# 10.3 Multiple Comparisons/ Multiplicity

No alpha adjustment for multiple comparisons will be introduced, because only the comparison between amifampridine and placebo group on the primary efficacy endpoint will be considered as confirmatory.

# 10.4 Examination of Subgroups

No subgroup analyses are foreseen for this study.

#### 10.5 Interim Analysis

There will be no Interim Analysis for this study.

### 10.6 Final Analysis

All final, planned analyses identified in this SAP will be performed by SPARC Consulting, Milan, Italy on behalf of Catalyst Pharmaceuticals following Sponsor Authorization of this Statistical Analysis Plan, Database Lock, Sponsor Authorization of Analysis Sets and Unblinding of Study Treatment.

## 10.7 Retests, Unscheduled Visits and Early Termination Data

In general, for by-visit summaries, data recorded at the nominal visit will be presented. Unscheduled measurements will not be included in by-visit summaries.

Listings will include scheduled, unscheduled and early discontinuation data.

### 10.8 Windowing Conventions

Actual dates of visits will be used for calculations of time intervals. No visit windowing will be performed for this study. Out-of-window visits will not be reallocated to the nearest timepoint.

## 10.9 Demographic Characteristics and Medical History

### 10.9.1 Demographic Characteristics

Demographic parameters, including age, gender, race, body weight, height, and BMI at Screening, will be summarized for the SAF analysis set.

## 10.9.2 Medical History

Summary analysis will involve the SAF analysis set.

SMA history parameters, including time in years from onset of SMA symptoms, previous treatments for SMA and SMN gene analysis results will be summarized by treatment sequence.

Time from onset of SMA symptoms will be calculated as the difference in years from the year of the date of informed consent and the year of onset of SMA symptoms reported in CRF.

All verbatim terms reported in the Medical History form will be assigned to a Preferred Term (PT) and will be classified by the primary System Organ Class (SOC) according to the Medical Dictionary for Regulatory Activities (MedDRA) thesaurus, version 23.

Previous diseases are those reported in the "Medical History" form of the eCRF with item "Present at study start?" flagged as "No".

Concomitant diseases are those reported in the "Medical History" form of the eCRF with item "Present at study start?" flagged as "Yes" or "Unknown".

The following data will be presented by treatment sequence:

- a) A default frequency table showing the number and percentage of patients who exhibited an abnormality by single body system;
- b) A default frequency table showing the number and percentage of patients who exhibited at least one previous disease and the previous diseases by primary SOC and PT;
- c) A default frequency table showing the number and percentage of patients who exhibited at least one concomitant disease and the concomitant diseases by primary SOC and PT;

Medical history will be listed for all enrolled patients.

## 10.10 Medication and Treatment Analysis

# 10.10.1 Patient Disposition and Accountability

The number and percentage of randomized patients who are in the SAF, FAS, and PPAS analysis set, and who complete each treatment period will be presented by treatment sequence. The number and percentage of patients who discontinue dosing prematurely, along with the primary reason that dosing was discontinued prematurely, will be presented by period and treatment at the time of discontinuation.

# 10.10.2 Duration of Treatment and Compliance

Duration of treatment during the open-label period will be summarized for the Safety Population. The duration of treatment during the open-label run-in period is the date of Day 0 minus date of first study dose+1.

Duration of treatment during the double-blind periods will be summarized for the Safety Population by treatment and by period and pooled.

For Period 1, the duration of treatment is the (date of Day 14 minus date of Day 0)+1; for patients who discontinue during Period 1, the duration of treatment during Period 1 is the (date of the last dose during Period 1 minus the date of Day 0) +1.

For Period 2, the duration of treatment is the (date of Day 28 minus date of Day 14)+1; for patients who discontinue during Period 2, the duration of treatment during Period 2 is the (date of the last dose during Period 2 minus the date of Day 14)+1.

The overall duration during the double-blind periods will be obtained for each treatment by adding the durations for the periods during which the patient received each treatment.

Compliance is 100%\*(Number consumed)/(Number prescribed). "Number consumed" is from Study Drug Accountability and "Number prescribed" is number of tablets to have been taken daily duration.

Compliance during the double-blind periods will be summarized for the Safety Population by treatment and by period. The compliance during the double-blind periods will be obtained for each treatment by performing the same calculations for the periods during which the patient received each treatment.

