Amifampridine dose will be titrated upward every 3 to 4 days, starting at 15 mg/day, at the discretion of the Investigator. Patients will either visit or have telephone/video contact with the site for each dose titration and at least one in-person site evaluation at Week 3 of the Runin period. When the Investigator determines that the patient has reached the maximal tolerable and efficacious dose, the patient should demonstrate they can remain on a stable dose and frequency for at least an additional 7 days. The Open-label Run-in period may be extended if additional time is needed for the dose titration. At the end of this period, patients must show at least a 3-point improvement in HFMSE score from start of Run-in, to be eligible for randomization (Day 0).

Randomization

Patients who continue to meet all the inclusion and exclusion criteria will be randomized on the last day of the Run-in period (Day 0).

Period 1 (Days 1-14) (± 1 day for each of Days 7 and 14)

Patients who have successfully completed the Open-label Run-in and continue to meet all inclusion/exclusion criteria will be randomized (1:1 ratio) on Day 0 to receive either

Page 27

amifampridine tablets (10 mg as amifampridine phosphate) or placebo tablets for 14 days, under double-blind conditions, (blinded medication to start after assessments obtained on open-label medication, on Day 0). Test medication will be dispensed by the Catalyst designee, according to the randomization schedule provided by Sponsor. All unused medication and the container must be brought back to the study site at each clinic visit. Safety and efficacy assessments will be made, in the site clinic, on Days 7 and 14 as detailed in the Schedule of Assessments in Table 1 and Section 12 STUDY Procedures.

Period 2 (Days 15-28) (±1 day for each of Days 21 and 28)

Following the in-clinic assessments on Day 14 of Period 1, the Period 1 study medication is collected and the patient should be given the blinded Period 2 medication; either amifampridine phosphate or placebo tablets (whichever they did not receive in Period 1) for 14 days. The Period 2 medication is to start with the next dose after the assessments are performed on Day 14 with Period 1 medication.

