9.3.3 Directions for Administration

All doses of study treatment will be taken at home, except one of the doses on the day of the in-clinic study visits, when it will be administered by study personnel and will be administered in the clinic to facilitate timing of efficacy assessments. Test medication should be taken every day at approximately the same time, at the dose and frequency instructed by Investigator. On the day of an in-clinic study visit (Days 0, 7, 14, 21, and 28), dose administration will be the medication the patient has been taking for the previous days, but administered by the study personnel 45 minutes before the first efficacy assessment. If the patient takes the dose three times a day, the patient should be given specific instructions on dosing relative to the time of their visit to assure a dose will be given during the in-clinic visit within the required time window. All safety assessments will be performed before the dose is administered to the patient during the in-clinic visit. Efficacy assessment will be performed at standardized times relative to the dose administered in the clinic.

Assessment	Start Time After Dose (+ 10 minutes unless otherwise specified)
HFSME	45 minutes
6-minute walk test	After HFSME
Time to rise from floor	After 6-minute walk
Time to rise from chair	After rise from floor
Time to climb 4 stairs	After rise from chair
Time to walk 10 meters	After climb stairs
Quality of Life Assessment	After 10-meter walk

The dose of amifampridine will be individually determined by the Investigator, within the bounds of a total daily dose of 15 mg to 80 mg, divided into doses taken 3 to 4 times per day as prescribed by the Investigator, based on optimal neuromuscular benefit. The maximum single dose is 20 mg. Amifampridine dose will be titrated upward every 3 to 4 days, starting at 15 mg/day, at the discretion of the Investigator. Pediatric dosing guidelines are presented in Table 2.

Table 2 Pediatric Dosing Guidelines

	Ages 6 to 16 Years	Ages >16 years
Recommended starting dose	5 mg, 3 times per day (15 mg/day total)	10 mg, 3 times per day (30 mg/ day total)
Initial dose escalation	May increase dose to 10 mg, 3 times per day (30 mg/day total)	May increase dose to 10 mg, 4 times per day (40 mg/day total)

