- INQoL for neuromuscular disease or the PEDSQLTM assessments will be completed for adult or pediatric patients, respectively after the six other assessments have been made.
- Randomization to Treatment Sequence

All open-label IP should be collected from the patient. The Investigator will dispense bottles containing amifampridine or placebo tablets, depending on the patient's randomization assignment, for daily outpatient administration for 14 days (Days 1-14), starting after completion of all assessments on Day 0.

Patients should be given a Drug Dosing Diary to record each dose of their double-blind medication and instructions on how to complete the form.

Patients continue administration of blinded study medication (amifampridine or placebo) until the Day 14 visit.

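### If SAP 10.10.2 multiplies daily tablets by its 15-date period count, a fully adherent completer scores 93.3% and the 80% compliance cut takes 85.7% of doses due (minor)

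*SAP*

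**What the plan says.** SAP 10.10.2 defines the double-blind durations by dates: "For Period 1, the duration of treatment is the (date of Day 14 minus date of Day 0)+1" and "For Period 2, the duration of treatment is the (date of Day 28 minus date of Day 14)+1". A patient who stops during Period 1 gets the same inclusive count up to the last dose: "date of the last dose during Period 1 minus the date of Day 0) +1".

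Compliance in that section is 100% times number consumed over number prescribed. The numerator comes from drug accountability. The denominator "is number of tablets to have been taken daily duration". No operator links the daily count to the duration. It may have been lost when the PDF was read, so its absence is not treated here as an error.

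The protocol describes the dosing as follows:

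- Section 12.3.1 (Day 0) dispenses Period 1 drug "for daily outpatient administration for 14 days (Days 1-14), starting after completion of all assessments on Day 0".
- Section 9.3.3 says that on a visit day "dose administration will be the medication the patient has been taking for the previous days". So the Day 0 clinic dose is open-label, and the Day 14 clinic dose is Period 1 drug.
- Section 9.1.1 labels the second period Days 15 to 28 and adds: "The Period 2 medication is to start with the next dose after the assessments are performed on Day 14 with Period 1 medication".
- Section 12.4 has Period 2 drug collected after the Day 28 assessments.
- Section 12.3.2 wants assessments tied to the same dose of the day at every visit. Section 12.4 does not repeat this for Period 2.

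An 80% cut appears twice in the SAP. Section 10.1 requires it of the doses required for the per-protocol set (PPAS). Section 10.13 expects overall compliance below 80% to count as a major deviation.

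**The concern.** The only durations that SAP 10.10.2 defines are its inclusive date counts, so a programmer completing the *Number prescribed* sentence would most naturally multiply daily tablets by them. Each period would then be charged 15 full days of tablets. Yet Day 0 and Day 14 are shared: part of each day's tablets belongs to the phase before the clinic dose and part to the phase after it.

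The compliance tables would then understate adherence for every completer, and the 80% cut in SAP 10.13 would be stricter than it looks. A patient above 80% of the doses due could be flagged as a major deviator and lost from the PPAS, which carries the supportive analysis of the primary endpoint.

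**Working it through.** **Inputs.** Nominal visits on Days 0, 14 and 28; 3 or 4 doses a day (SAP 5.3); duration formulas from SAP 10.10.2. Assumptions: *Number prescribed* is daily tablets x SAP duration, tablets per dose are equal, and clinic-given doses are counted in accountability.

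**Duration by the SAP formula.** Period 1: 14 - 0 + 1 = 15. Period 2: 28 - 14 + 1 = 15.

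**Doses due under the protocol.** Let there be D doses a day, with the clinic dose in position k at both ends of a period. Then D - k doses remain on the first day, 13 full days follow, and k doses fall on the last day:

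(D - k) + 13D + k = 14D

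This reproduces the protocol's 14 days for any k: 42 doses at 3 a day, 56 at 4 a day.

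**Score at full adherence, per period.** 14D / 15D = 42/45 = 56/60 = 93.3%.

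**Adherence needed to show 80% over both periods.** 0.80 x 30D / 28D = 85.7% of doses due. A patient who took exactly 80% of doses due would show 0.80 x 28/30 = 74.7%.

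**Who would be flagged although at or above 80% of doses due.**

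| Doses a day | Due, both periods | Denominator | Doses taken | Share of due | Compliance shown |
|---|---|---|---|---|---|
| 3 | 84 | 90 | 68 to 71 | 81.0% to 84.5% | 75.6% to 78.9% |
| 4 | 112 | 120 | 90 to 95 | 80.4% to 84.8% | 75.0% to 79.2% |

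**Sensitivity.**

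- *Visit windows of ±1 day.* A period spans 12 to 16 days between visits. Full adherence scores 12/13 = 92.3% to 16/17 = 94.1%. With 27 to 29 days over both periods, the threshold runs from 0.80 x 29/27 = 85.9% to 0.80 x 31/29 = 85.5%.
- *Clinic-dose position differs between visits.* At nominal dates, full adherence in one period scores 40/45 = 88.9% to 44/45 = 97.8% (3 a day) or 53/60 = 88.3% to 59/60 = 98.3% (4 a day). The two-period threshold is 72/82 = 87.8% to 72/86 = 83.7%, or 96/109 = 88.1% to 96/115 = 83.5%.
- *Direction.* With G days from the Day 0 to the Day 28 visit and a net position shift of j doses, the threshold is 0.80 x D(G + 2)/(DG + j). Since j is at most D - 1, which is less than 2D, it always exceeds 80%.
- *A different overall denominator.* A single Day 0 to Day 28 count of 29 dates would give 28/29 = 96.6% at full adherence and a threshold of 0.80 x 29/28 = 82.9%. Including the run-in would change the size again; its length is not fixed, so no figure is given.
- *Denominator is tablets due.* Full adherence scores 100%, and the cut is 80% of doses due.

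**The case against.** The strongest reply is that the point rests on a sentence that cannot be read as it stands. The multiplication and the link to the +1 duration both have to be supplied. Tablets that were to have been taken could equally mean tablets due, and then nothing is wrong. This stands, and it is why the point is conditional. It does not remove the need to settle the sentence, because the section offers no other duration.

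Four stronger inferences are tempting, and the documents support none of them:

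- *The 15-day formula is itself wrong.* Blinded drug starts after the Day 0 assessments and runs through the Day 14 clinic dose, so doses fall on parts of 15 dates. As a count of dates the formula is sound.
- *SAP 10.1 and 10.13 contradict each other.* They conflict only if one uses doses due and the other the larger denominator. Neither cites 10.10.2, so this cannot be shown.
- *Patients would be excluded automatically.* SAP 10.13 has the clinical team discuss each deviation individually before database lock, and it only anticipates that low compliance will be major.
- *The plan credits a treatment with 30 days.* Each treatment fills one period per patient, and the pooled summary is not defined.

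The flagged band is also narrow, 4 to 6 doses wide, and the documents give no expected adherence from which to say how many patients would fall in it.

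**Conclusion.** The point holds conditionally and is minor. If *Number prescribed* is daily tablets x the SAP duration, the denominator is one day's tablets too large in each nominal period when the clinic dose keeps its position in the day. Full adherence then shows 93.3%, and 80% over the two double-blind periods takes 85.7% of doses due. A patient who took from 80% to just under 85.7% of doses due could be flagged under SAP 10.13, subject to blind review.

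The 85.7% figure assumes that overall compliance means the two double-blind periods added together, which SAP 10.13 does not say. Other definitions change the size, as shown above.

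Only the compliance summaries and the supportive PPAS analysis could be affected. A reader might infer a threat to the main efficacy result, but SAP 10.11 makes the full analysis set primary, and compliance does not enter it. For scale, one wrong exclusion among about 12 patients would remove 1/12 = 8.3% of the supportive set.

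**What to change.** Amend the SAP wording in two places:

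- *Section 10.10.2.* Define *Number prescribed* as the tablets scheduled from the first due dose after the period-start clinic visit through the period-end clinic dose, or through the last due dose before discontinuation. For a nominal completer this is 14 x daily tablets. Say that the +1 duration is not the multiplier.
- *Sections 10.1 and 10.13.* State that both 80% rules use this denominator, and which study phases overall compliance covers.

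Leave the duration formulas unchanged and describe them as counts of calendar dates with any dose. Dropping the +1 would give 0 days to a patient who takes one blinded dose on Day 0 and stops.

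The cost is a few sentences, plus programming scheduled doses per patient instead of taking them from visit dates. No new data are needed if the prescribed regimen, clinic-dose time and discontinuation date are recorded. The SAP introduction already provides for review and revision before the final unblinded analyses.

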#### 10.10.3 Concomitant Medications

All prescription and over-the-counter medications and herbal and nutritional supplements taken by a patient for 14 days before the Screening visit will be recorded on the designated CRF. Additionally, the stop date of any medications the patient was taking within 6 months before Screening that are excluded or restricted by the protocol will be recorded.

The Investigator may prescribe additional medications during the study, if the prescribed medication is not prohibited by the protocol. In the event of an emergency, any needed medications may be prescribed without prior approval, but the medical monitor must be notified of the use of any contraindicated medications immediately thereafter. Any concomitant medications added or discontinued during the study should be recorded on the CRF.

Concomitant medications will be only listed for all enrolled patients.

# 10.11 Efficacy Analyses

The primary assessment of efficacy will be performed using the CFB in HFMSE total score. Secondary assessments of efficacy will be performed using the following endpoints:

- 1. CFB in 6-minute walk test (meters);
- 2. CFB in rising from floor (seconds);
- 3. CFB in rising from a chair (seconds);
- 4. CFB in climbing 4 steps (seconds);
- 5. CFB in walking 10 meters (seconds);
- 6. CFB in the INQoL subscales scores:

Symptoms (section 1):

- a) Weakness
- b) Muscle "locking"
- c) Pain
- d) Fatigue
- e) Droopy eyelids
- f) Double vision
- g) Swallowing difficulties

Life domains (section 2):

- a) Activities
- b) Independence
- c) Social relationship
- d) Emotions
- e) Body image

Life domains (section 3):

- a) Perceived treatment effects
- b) Expected treatment effects

Quality of Life

7. CFB in the PEDSQL score (where applicable).

The individual domain scores in INQoL and PedsQL will be calculated using the scoring algorithms outlined in Appendix 2.

The efficacy assessments will be summarized by sequence and period.

The change-from-baseline scores [Change From Baseline (CFB)7 = HFMSE7 – HFMSE0, CFB14 = HFMSE14 – HFMSE0, CFB21 = HFMSE21 – HFMSE0, CFB28 = HFMSE28 – HFMSE0] will be analyzed using a mixed effects linear model. Treatment (amifampridine (A) or placebo (P)) and Sequence (A/P or P/A) and the Treatment by Sequence interaction will enter the model as fixed effects. Subject within Sequence will enter the model as a random effect with a block diagonal covariance structure. The 95% confidence interval (CI) based on this model will be presented for the difference in the Least Squares (LS) means. The analysis will be performed using SAS PROC MIXED to incorporate the random effects model.

A summary statistics on the CFB in the individual items score of the HFMSE will be also provided by sequence and period.

The quantitative secondary efficacy endpoints (6-minute walk test, Time-to-rise-from-floor, Time-to-rise-from chair, Time-to-climb-4-stairs, and Time-to-walk-10 meters) will be analyzed as the HFMSE is analyzed. The four CFB scores will be analyzed with a linear mixed model. Treatment and Sequence will be entered as fixed effects. Subject within Sequence will be entered as a random effect with a block-diagonal covariance structure. The 95% confidence interval (CI) based on this model will be presented for the difference in the Least Squares (LS) means. The analyses will be performed using SAS PROC MIXED to incorporate the random effects model.

Results from INQoL questionnaires and PEDSQL inventory of disease specific symptoms will be summarized with descriptive statistics (n, mean, standard deviation, minimum, median, and maximum) per time point (Days 0, 7, 14, 21, and 28) and CFB, using the Day 0 response as the baseline level). The subscales of the INQoL questionnaires will be similarly summarized.

Analysis of the primary efficacy endpoint will be perfored both in the FAS and in PPAS analysis set. Analysis on FAS analysis set will be considered as primary while analysis in the PPAS will be used as supportive of the FAS results.

Analysis of secondary efficacy endpoints will be performed only in the FAS analysis set.

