two years of age. SMA Type 2 also presents very early, before 18 months of age, but symptoms are less severe, and these children are able to sit or even to stand unsupported, although they do not achieve the ability to walk independently. SMA Types 3 and 4 are the least severe forms. In Type 3, symptoms appear after 18 months of age, and severity is highly variable. Many patients have only proximal muscle weakness and can stand and walk independently, sometimes until the late disease stages. Life expectancy is near normal. SMA Type 4 has an adult onset, sometimes after 30 years of age, and muscle weakness, mainly of proximal muscles, is relatively mild and slowly progressing, although loss of independent walking has been rarely reported (Shababi 2014).

SMN protein localized in the presynaptic terminals at the neuromuscular junction (NMJ) (Dombert 2014) and its role in NMJ development has been tested by the failure of the cultured muscle cells derived from SMA patients to cluster acetylcholine receptors (AChRs) at the junction (Arnold 2004). In addition, neurofilament accumulation along with poor terminal arborization in postnatal diaphragm samples of SMA Type 1 have been reported (Kariya 2008). Further evidence for a possible role of abnormal NMJ in human SMA pathology derives from a recent study providing a detailed structural characterization of NMJ defects in SMA fetuses (Martinez-Hernandez 2013); main prenatal defects were abnormal modification of acetylcholine receptor clustering, irregular accumulation and positioning of synaptic vesicles, and atypical nerve terminals in motor endplates of SMA Type 1 samples, whereas SMA Type 2 fetuses were similar to controls.

In SMA mice some findings suggest skeletal muscle fiber disruption, such as increased activity of cell death pathways (Mutsaers 2011), abnormal differentiation in muscle satellite cells, deficient formation of myotubes, and decreased muscle fiber size (Lee 2011; Hayhurst 2012). Interestingly, loss of murine SMN specifically in the skeletal muscle causes muscle necrosis, paralysis, and death (Cifuentes-Diaz 2001).

In addition, restoration of SMN in the mature muscle or increasing the muscle mass through different molecules have limited therapeutic benefits in SMA mice (Gavrilina 2008; Rose 2009; Bosch-Marce 2011), further confirming that NMJ maturation defects and abnormal synapses are the hallmark of SMA pathology (Kariya 2008).

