9.2.1 Inclusion Criteria

Individuals eligible to participate in this study must meet all the following inclusion criteria:

- 1. Willing and able to provide written informed consent after the nature of the study has been explained and before the start of any research-related procedures.
- 2. Male or female between the ages of 6 and 50 years.
- 3. Genetically confirmed diagnosis of SMA Type 3.
- 4. Able to walk independently for at least 30 meters (objectively measured at screening).
- 5. Not taking Nusinersen for the treatment of SMA (Nusinersen should be stopped at least 6 months before the screening). Salbutamol is permitted only if the dose has been stable for 6 months before screening.
- 6. Able to swallow oral medication.
- 7. Female patients of childbearing potential must have a negative pregnancy test (serum human chorionic gonadotropin [HCG] at screening); and must practice an effective, reliable contraceptive regimen during the study and for up to 30 days following discontinuation of treatment.
- 8. Ability to participate in the study based on overall health of the patient and disease prognosis, as applicable, in the opinion of the Investigator; and able to comply with all requirements of the protocol, including completion of study questionnaires.

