275tand to sit	Can you sit on the floor, in a controlled way? Try not to use your arms.	Able to sit down with arms free and no collapse	Sits on floor but uses arms or crashes	Unable			
28Squat	Can you squat? Pretend you are going to sit in a very low seat.	Squats with arms free (at least 90° of hip and knee flexion)	Initiates squat (more than 10%) , uses arm support	Unable to initiate			
29 Jump 12" forward	Can you jump as far as you can, with both feet, from this line all of the way to the other line?	Jumps at least 12", both feet simultaneously	Jumps between 2-11", both feet simultaneously	Unable to initiate jump with both feet simultaneously	2		
30 Ascends stairs with rail	Can you walk up the steps? You can use one railing	Ascends 4 stairs with railing, alternating feet	Ascends 2-4 stairs, one rail, any pattern	Unable to ascend 2 stairs one rail			
31 Descends stairs with rail	Can you walk down the steps? You can use one railing	Descends four stairs , with railing, alternating feet	Descends 2-4 stairs, one rail, any pattern	Unable to descend 2 stairs with one rail	l IV		
32 Ascends stairs without rail	Can you walk up the steps? This time try not to use the railing	Ascends four stairs, arms free, alternating feet	Ascends 2-4 stairs, arms free, any pattern	Unable to ascend 2 stairs arms free			
33 Descends stairs without rail	Can you walk down the steps? This time try not to use the railing	Descends four stairs, arms free, alternating feet	Descends 2-4 stairs, arms free, any pattern	Unable to descend 2 stairs arms free			
SCORE		No of 2's =	No of 1's =	No of o's =			TOTAL = /66

Page 70

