#### 9.1.3 Timed items

a) Rising from floor – the time required in rising from the supine position

- b) Rising from a chair the time required to stand from a seated position
- c) Climbing 4 steps the time required to climb 4 standardized steps
- d) Walking 10 meters the time required to walk 10 meters as fast as possible

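### Floor rise, chair rise and 4-step climb are analyzed in raw seconds with no rule for a patient who tries and cannot complete the test, so a loss of ability (on placebo or on drug) has no value in the analysis

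*SAP*

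**What the plan says.** SAP 10.11 puts all four timed tests on a seconds scale, for example "CFB in rising from floor (seconds" and "CFB in climbing 4 steps (seconds". SAP 9.1.3 defines each item as elapsed time only; floor rise is "the time required in rising from the supine position". For the analysis, "The four CFB scores will be analyzed with a linear mixed model", and "Analysis of secondary efficacy endpoints will be performed only in the FAS analysis set", so no supportive analysis is planned. Protocol 14.6.2 has the same plan.

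Neither document gives a maximum time, an assigned value, a conversion to speed, a rank analysis or a code for inability on these tests. SAP 11.2 (missing data) deals with discontinuation and the INQoL only.

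The functional entry criterion is "Able to walk independently for at least 30 meters (objectively measured at screening" (Protocol 9.2.1). Nothing is required about rising or stairs. Baseline is Day 0 (SAP 10.2), measured after a clinic dose of open-label amifampridine (Protocol 12.3.1), in patients who gained at least 3 HFMSE points during run-in (Protocol 9.2.2, SAP 7.2).

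**The concern.** Inability is foreseeable in this population. Protocol 7.1 says "Many patients have only proximal muscle weakness and can stand and walk independently", and these three tests load the proximal muscles. The protocol's own HFMSE form provides for failure on related tasks, such as "Unable to ascend 2 stairs one rail", and on kneel-to-stand. The HFMSE scores inability as 0 and so keeps the patient (SAP 9.1.1); the timed tests have no equivalent.

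The design makes the gap matter. Patients enter the double-blind phase on drug, so the comparison is largely about function lost on placebo. Able on drug and unable on placebo is the largest contrast a timed test can show, yet on a seconds scale it produces no placebo value. Such missingness depends on the unobserved outcome, and a likelihood-based mixed model treats it as ignorable. Inability on amifampridine disappears in the same way, so harm can also be hidden.

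**Working it through.** The documents give no inability rate, time distribution or power calculation for these tests, so there is no figure of the plan to reproduce. From the documents come 12 patients, 6 per sequence, and change scores at Days 7, 14, 21 and 28. Every time, limit and effect below is an assumption.

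**1. Which values exist.** Change score = time at visit − time at Day 0.
- Unable at Day 0: no Day 0 time, so none of the four change scores, even if able later.
- Able at Day 0 and on drug, unable at both placebo visits: two drug scores, no placebo score, and essentially nothing for the within-patient contrast. A patient who fails only one placebo visit keeps the other.
- Able on placebo, unable on drug: the mirror image.

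**2. Abrupt loss of ability.** Assume 8 s on drug, 9 s on placebo if still able, and k of 12 patients unable on placebo.
- Observed seconds: 9 − 8 = 1.0 s, from 12 − k patients.
- Unable set to an assumed 30 s: [(12 − k) × 1 + k × 22] / 12.
- Speed with unable = 0: [(12 − k)(1/9 − 1/8) + k(0 − 1/8)] / 12.

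| k | Observed seconds (patients) | 30 s assigned | Speed (per s) |
|---|---|---|---|
| 0 | 1.0 (12) | 1.00 | −0.014 |
| 1 | 1.0 (11) | 2.75 | −0.023 |
| 2 | 1.0 (10) | 4.50 | −0.032 |
| 3 | 1.0 (9) | 6.25 | −0.042 |
| 4 | 1.0 (8) | 8.00 | −0.051 |

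The planned scale gives the same answer however many patients lose the ability.

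**3. Times that drift past a limit.** Assume placebo times T are log-normal (median 12 s, log SD 0.8), drug time = 0.82 T, and inability beyond a limit c. With no visit-to-visit noise, the mean difference is −0.18 × E[T | T < c] in patients measured on both treatments, and −0.18 × E[T | T < c/0.82] in all patients able on drug.

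| c | Both measured | All able on drug | Understated | Able only on drug, of 12 |
|---|---|---|---|---|
| 20 s | −1.76 s | −1.96 s | 10% | 0.9 |
| 30 s | −2.16 s | −2.34 s | 8% | 0.5 |
| 60 s | −2.70 s | −2.79 s | 3% | 0.1 |

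Adding visit-to-visit noise with log SD 0.2 raises the understatement to about 35%, 26% and 11%.

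**4. The planned type of model.** A small simulation (120 runs per setting) fitted a random-intercept mixed model with treatment and sequence to the four change scores, with inability beyond 30 s. About 0.7 to 3.5 of 12 patients were unable at Day 0. With true slowing of 15% to 50% on placebo, a further 0.5 to 3.1 failed at least one placebo visit. At a 20 s median and 15% slowing, power was 0.66 for raw seconds, 0.70 with a 30 s cap and 0.72 for speed. The simulation error is about √(0.7 × 0.3 / 120) = 0.04, the same order as those differences. The raw-seconds mean difference was similar to or larger than the capped one, because patients unable at Day 0 leave the raw analysis and the cap shortens long times.

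**The case against.** The strongest reply is that this is a silence in minor endpoints. Only the primary comparison is confirmatory (SAP 10.3), in a Phase 2a trial without a power calculation. The HFMSE keeps inability as 0 and includes stair and kneel-to-stand items. Non-missing counts and full listings are planned (SAP 10.2), so losses would be visible. All of this stands, and it limits the weight of the point. It does not supply a value for the patient who cannot complete the test.

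Three stronger readings are tempting, and the documents do not support them.
- *The trial discards its best evidence of benefit.* Part of that signal stays in the HFMSE. A patient unable at Day 0 is unable on titrated open-label drug, which is not discarded evidence of benefit. Nor do the documents say that inability is recorded as missing: they are silent, and the case report form and table shells are not in the reviewed text.
- *The effect is understated by a quarter or a third.* Figures of that size need substantial visit-to-visit noise. They also need a comparator that selects on the drug time alone and uses placebo times beyond the limit, which nobody could observe.
- *The bias is always towards zero.* The mixed-model simulation does not show this when times only drift.

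Speed can also be criticized. Going from 20 s to unable changes 1/time by 1/20 = 0.050, while slowing from 3.0 to 3.66 s changes it by 1/3.0 − 1/3.66 = 0.060, so fast patients carry more weight. In a paired check under the step 3 inputs (two visits per treatment, log SD 0.15), power for seconds versus speed was 0.82 and 0.84 at a 20 s limit, 0.88 and 0.86 at 30 s, and 0.88 and 0.85 at 60 s. Speed is therefore a way to keep these patients in the analysis, not a reliable gain in power.

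**Conclusion.** The point holds for rise from floor, rise from chair and the 4-step climb. Followed as written, the plan gives no value to an attempted but uncompleted test and relies on a model that assumes such gaps are ignorable. The size cannot be fixed from the documents. If times only drift past a limit, it is small: roughly 3% to 10% without visit-to-visit noise, more with it, and little change in power. If ability is lost abruptly, the planned estimate does not register the loss at all, in either direction. These ranges rest on assumed times, limits and effects.

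The 10 m walk is largely protected by the 30 m entry test, and the 6-minute walk is in meters, where 0 can be recorded. This is a worthwhile correction to non-confirmatory secondary endpoints; it does not threaten the primary analysis.

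**What to change.** SAP section 4 already allows revision before the final unblinded analyses. Amend 10.11 then, for the three tests:
- Record an attempted but uncompleted test as unable, distinct from not done.
- Analyze speed (1/time for the two rises, steps per second for the climb) with unable = 0, using the same mixed model, at minimum as a pre-specified companion to the seconds analysis.
- Tabulate the number unable by treatment and visit.

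Apply the same rule to the 10 m walk only as a precaution.

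The cost is one derived variable, one table and a few lines of SAP text, with no new tests. It does require that site records distinguish unable from not done. The downsides are results in speed units, more weight on fast patients, and similar or slightly lower power where inability is rare. Fixing the rule before unblinding also removes a post hoc choice.
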